572 **Subject Compliance**

573 We estimate that the majority of the participants who will be considered eligible will
574 complete the study. Attrition can be estimated as lower than 10%. In the event that
575 participants are lost to follow-up, the research coordinator will contact with the study
576 participant by telephone. The research coordinator will be trained in effective telephone
577 technique to maximize recruitment success. All groups will receive lifestyle and diabetes
578 education, as part of the standard care, to insure similar glycemic control between arms.
579 Study patients will be advised to monitor their capillary glucose twice daily, fasting in the
580 morning and post-prandially. Glucose profile will be tracked bi-weekly by the research
581 coordinator by email or telephone.

582

583 **Statistical Considerations**

584 POWER ANALYSIS

585 The statistical power (two-sided, $\alpha=0.05$) of the study was calculated to detect statistically
586 and clinically meaningful differences in the primary endpoint between the two study arms.
587 Our preliminary data showed that EAT inflammatory genes, including IL-6 and TNF- α are
588 upregulated in subjects with T2DM and CAD and higher in EAT as compared to SAT⁴⁻¹⁷.
589 From our recently published study, we calculated the average coefficient of variance (CV)
590 for differential inflammatory genes to be 42%, but for only 5 T2DM patients.¹⁷ As there
591 are no data on the effects of liraglutide on EAT inflammation, the power analysis was based
592 on our previous data and on the assumption that the difference in EAT TNF- α and IL-6
593 expression between liraglutide treated and placebo treated patients would be clinically
594 meaningful at 33% (approx. 1.3X fold). Based on these data, we propose to sample 40
595 individuals. There will be 20 on liraglutide plus standard therapy versus 20 subjects on
596 liraglutide-matching placebo plus standard therapy contributing EAT and SAT samples
597 collected during cardiac surgery. Using the power set at 90% and $\alpha=0.05$, and given the
598 CV of 42%, this sample size will provide adequate power to detect the clinically significant
599 expected difference (33%) in EAT TNF- α and IL-6 between the two study arms.

600 Based on pre-existing data, this sample size will provide adequate power to detect
601 statistically significant differences in EAT TNF- α and IL-6 between the two study arms in
602 those patients who will receive treatment only for 3 weeks. The difference in EAT TNF- α
603 and IL-6 between liraglutide treated and placebo treated patients is expected to be
604 approximately 1X fold after 3 weeks of treatment.

605

606 The larger sample proposed in this current project would likely reduce the variability. To
607 further assure consistency of results, mRNA and protein expression values will be log-

608 transformed prior to statistical analyses unless they will be normally distributed.
 609 Housekeeping genes will be also used for both RT-PCR and western blot analyses.
 610 In those patients who will not complete the 12-week treatment, the analysis of EAT genes
 611 from the samples will be time adjusted

612
 613 Statistical power was also calculated to detect statistically significant differences in the
 614 ultrasound measured EAT thickness, secondary endpoint, between the two study arms Our
 615 group very recently showed that additional therapy with liraglutide for 12 weeks caused a
 616 reduction in ultrasound measured EAT from 9.6 ± 2 to 6.2 ± 1.5 mm ($p < 0.001$) in 54 patients
 617 with T2DM ¹¹. Given the reference value and the expected difference in EAT, the
 618 statistical power of the study (two-sided, $\alpha = 0.05$) was calculated.

619

Outcome	Reference value \pm SD	Expected Difference	Detectable difference with 80% power $\alpha = 0.05$	Detectable difference with >99% power $\alpha = 0.05$
EAT (mm)	9.6 ± 2	-20-or -30%	-20% (absolute difference = 1.9)	-30% (absolute difference = 2.88)

620

621 Assuming a difference of approximately 2 mm (20%) in EAT to be clinically significant
 622 (based on our recent and previously published data ¹⁰⁻¹⁴), a convenience sample of 20
 623 individuals for each group will therefore provide at least the statistical power (80%) to
 624 detect an expected difference of at least -20% in the EAT before and after treatment with
 625 liraglutide. Baseline standard Deviation (SDs) of 2 is expected to lower to approximately
 626 1.5 for the expected change. The expected change of SD will further assure significant
 627 statistical power of the comparative test.

628

629 In those study patients who will not be able to complete the 12-week treatment, we
 630 anticipate to see a 15% of EAT reduction after 3 weeks in patients who will be allocated to
 631 liraglutide. This anticipated 15% of EAT reduction will remain clinically significant. For
 632 example, a EAT thickness of 10 mm may likely decrease to 8.5 mm after 3 weeks of
 633 treatment with liraglutide, a clinically meaningful change for the patient cardio-metabolic
 634 profile.

635

636 This sample size also considers the difficulties with recruitment in the real world clinics.
 637 Based on our previous studies in humans, some participants may be lost to follow-up.

638

639 Student's t-test or non-parametric (Mann-Whitney) tests, depending on whether the genes
 640 mRNA expression and protein present or not a normal distribution, will be used to compare
 641 the effects of treatment (liraglutide versus placebo) on the variables measured. Student's
 642 t-test will be also used to compare ultrasound measured EAT thickness before and after
 643 treatments. Continuous variables will be considered as age-adjusted, sex-adjusted and
 644 weight-adjusted means with their SDs or median, if values are skewed.

645 Univariate regression models will be performed to assess the correlation between clinical
646 variables, including echocardiographic EAT thickness and blood tests, and EAT gene and
647 protein expression. Two-tailed $p < 0.05$ indicates statistical significance.

648

649 **Data Handling and Record Keeping**

650 Each of the dedicated clinic exam rooms provides direct access to the clinical research
651 study electronic data capture (EDC) eVelos system provided by the Clinical Research
652 Informatics and Data Management Unit of the Center for Health Informatics and
653 Bioinformatics at University of Miami (UM). The investigator and research coordinator
654 will collect and manage the data.

655 Data collection records with personal identifiers will be stored in locked file cabinets, at
656 [name]. Blood samples drawn
657 and stored in conjunction with this study will not be labeled with information that could
658 directly identify study subjects. Presentation of the study results at scientific meetings or
659 in publications will not identify subjects. Access to research and confidential records will
660 be limited to clinical investigators, research coordinators, and the IRB at UM.

661 **Adipose tissue samples storing**

662 Each adipose tissue sample will be snap frozen in liquid nitrogen and stored at -80°C until
663 analysis in a freezer, in [name] lab, University of Miami, Dept of Microbiology, 1600
664 [name]. Once the sample is taken, it will be unlinked from
665 patient's name. This will assure confidentiality and anonymity. Current or future research
666 on adipose tissue samples will need to be approved by the local IRB.

667

668 **Ethical Considerations**

669 The study has been approved by the UM local institutional review board (IRB). The study
670 will be conducted in accordance with the Declaration of Helsinki. The study will be
671 conducted in accordance with the ICH GCP guidelines. The investigator will comply with
672 all applicable regulatory and legal requirements, ICH GCP guidelines and the Declaration
673 of Helsinki in obtaining and documenting the informed consent.

674 **Informed Consent:** Eligible and willing participant will be approached by the
675 investigators or the research coordinator and consented. Written informed consent form
676 will be obtained from the subjects before "baseline" activities begin. Each patient will sign
677 and date the informed consent. As standard procedure, patients will be informed of the
678 risks and complications related to cardiac surgery, regardless of their participation in the
679 study.

680

681

682 **Study Schedule**

683 Expected milestones:

- 684 • start of study: 09/01/2017

685 • first patient first visit 09/01/2017
686 • last patient last visit 10/31/2023
687 • Planned completion of integrated final study report 12/2023

688

689 **Study Drugs and Materials**

690 **Trial drugs**

691 Trial drugs will be supplied as liraglutide and matching liraglutide-placebo pre-filled pens
692 for subcutaneous injection, provided by Novo Nordisk. Pre-filled, multi-dose pen for
693 subcutaneous injection delivers doses of 0.6 mg, 1.2 mg, or 1.8 mg (6 mg/mL, 3 mL).

694 **Labelling of trial drugs:** All the pre-filled pens will be labeled “liraglutide/placebo”

695 **Trial drugs supply** Trial drugs (liraglutide and matching placebo) will be supplied to each
696 study subject by Novo Nordisk.

697 Clinical Supply in Novo Nordisk Headquarter will revert with timeline for delivery of trial
698 drugs when protocol is approved, and Novo Nordisk Headquarter will receive a signed
699 contract and other additional information. Standard delivery is 4 months.

700 **Storage and Drug Accountability of Study Medication**

701 The investigator will ensure the availability of proper storage conditions and record and
702 evaluate the temperature. Prior to first use, trial drugs will be stored in a refrigerator
703 between 36°F to 46°F (2°C to 8°C). After initial use of the trial drug pen, the pen can be
704 stored for 30 days at controlled room temperature (59°F to 86°F; 15°C to 30°C) or in a
705 refrigerator (36°F to 46°F; 2°C to 8°C). Trial drugs will be not dispensed to any person not
706 enrolled in the study. Unused trial drugs will be stored separately from used trial
707 medication.

708 **Randomization and Blinding**

709 This will be a double-blind, parallel group, placebo controlled study. The method of
710 allocation generation will be a computerized random-number generator. The sequence will
711 be generated by the process of restricted randomization. Computer-based randomization
712 process will be managed by the UM Research pharmacy.

713

714 **Concomitant Illnesses and Medications**

715 **Background medications:**

716 **Metformin.** Metformin is considered background medication (non-investigational
717 medicinal product) and will not be provided during the trial. Dose adjustments could occur
718 during the trial at the investigator’s discretion. As [name] et al ¹² recently showed no
719 significant effects of metformin on EAT, we do not anticipate that metformin dose
720 adjustment may influence the study outcomes.

721 **Long acting insulins.** Insulin is considered background medication (non-investigational
722 medicinal product) and will not be provided during the trial. The total daily dose of insulin
723 could be adjusted during the trial at the investigator’s discretion. [name]’ group recently
724 performed a 24-week interventional study to compare EAT changes in insulin-naïve

725 inadequately controlled patients with type 2 diabetes following basal insulin initiation with
726 detemir vs. glargine. No significant changes in EAT between detemir and glargine were
727 observed. ²¹ Based on these findings we do not anticipate that insulin treatment may
728 influence the study outcomes.

729 **Sulfonylureas.** Sulfonylurea treatment is considered background medication (non-
730 investigational medicinal product) and will not be provided during the trial. During the
731 study, no up-titration of sulfonylurea dosage will be allowed. Dose reduction of SU due to
732 hypoglycemia may be allowed at the investigators discretion. In the event of
733 hypoglycemia, the dose of sulfonylurea can be reduced or the drug can be stopped at the
734 investigator's discretion.

735 **Adverse Events**

736 In the case of an adverse event (AE), the investigator will comply with all local legal,
737 regulatory, and IRB requirements. The investigator will report to IRB all adverse events
738 including not serious and serious adverse events (SAE), suspected unexpected serious
739 adverse reactions (SUSARs), serious adverse drug reactions (SADRs). The investigator
740 will report all SAEs, SUSARs, and SADRs at the same time such events are reported to
741 regulatory authorities or within 15 days from the investigator becoming aware of such
742 adverse events, whichever comes first.

743 The investigator will use the approved Updated Prescribing Information for Victoza®. The
744 investigator will collect the following information at minimum for each of these events: 1.
745 Study name2. Patient identification 3. Event (preferably a diagnosis) 4. Drug 5. Reporter
746 identification. 6. Causality 7. Outcome

747 **Definitions** An AE is any undesirable medical event occurring to a subject in a clinical
748 trial, whether or not related to the trial product(s). This includes events reported from the
749 first trial related activity after the subject has signed the informed consent and until post
750 treatment follow-up period as defined in the protocol. The following should not be recorded
751 as AEs, if recorded as medical history/concomitant illness at screening:
752 • Pre-planned procedure, unless the condition for which the procedure was planned has worsened from
753 the first trial related activity after the subject has signed the informed consent
754 • Pre-existing conditions found as a result of screening procedures

755 Clinical Laboratory Adverse Event: A clinical laboratory AE is any clinical laboratory
756 abnormality regarded as clinically significant i.e. an abnormality that suggests a disease
757 and/or organ toxicity and is of a severity, which requires active management, (i.e. change
758 of dose, discontinuation of trial product, more frequent follow-up or diagnostic
759 investigation).

760 **Serious Adverse Event (SAE):** A serious AE is an experience that at any dose results in
761 any of the following:

- 762 • Death
- 763 • A life-threatening* experience
- 764 • In-patient hospitalization or prolongation of existing hospitalization

765 Suspicion of transmission of infectious agents must always be considered an SAE
766 • A persistent or significant disability/incapacity
767 • A congenital anomaly/birth defect
768 • Important medical events that may not result in death, be life-threatening*, or require
769 hospitalisation may be considered an SAE when, based upon appropriate medical
770 judgement, they may jeopardise the subject and may require medical or surgical
771 intervention to prevent one of the outcomes listed in this definition

772 *The term life-threatening in the definition of SAE refers to an event in which the subject
773 was at risk of death at the time of the event. It does not refer to an event which
774 hypothetically might have caused death if it was more severe.

775 **SADR:** an adverse drug reaction (ADR) is an adverse event for which a causal relationship
776 (Possible/Probable relation) between the study drug and the occurrence of the event is
777 suspected. The ADR should be classified as serious if it meets one or more of the
778 seriousness criteria.

779 **Medical Events of Special Interest (MESI):** A MESI is (1) a medication error (e.g. wrong
780 drug administration or wrong route of administration) or (2) a suspected transmission of an
781 infectious agent via the product

782 **Non-Serious Adverse Event:** A non-serious AE is any AE which does not fulfil the
783 definition of an SAE. Severity Assessment Definitions:

- 784 • Mild: Transient symptoms, no interference with the subject's daily activities
- 785 • Moderate: Marked symptoms, moderate interference with the subject's daily activities
- 786 • Severe: Considerable interference with the subject's daily activities, unacceptable

787 Relationship to study medication Assessment Definitions:

- 788 • Probable: Good reasons and sufficient documentation to assume a causal relationship
- 789 • Possible: A causal relationship is conceivable and cannot be dismissed
- 790 • Unlikely: The event is most likely related to an etiology other than the trial product

791 **Outcome Categories and Definitions:** • Recovered: Fully recovered or by medical or
792 surgical treatment the condition has returned to the level observed at the first trial related
793 activity after the subject signed the informed consent• Recovering: The condition is
794 improving and the subject is expected to recover from the event. This term should only be
795 used when the subject has completed the trial • Recovered with sequelae: As a result of the
796 AE, the subject suffered persistent and significant disability/incapacity (e.g. became
797 blind, deaf, paralysed). Any AE recovered with sequelae should be rated as an SAE• Not
798 recovered• Fatal• Unknown

800 **Collection, Recording and Reporting of Adverse Events:** All events meeting the
801 definition of an adverse event will be collected and reported from the first trial related
802 activity after the subject has signed the informed consent and until the end of the post-
803 treatment follow-up period as stated in the protocol.

804 **Follow-up of Adverse Events:** During and following a subject's participation in a clinical
805 trial, the investigator and institution will provide adequate medical care to the study subject

806 for any study-related adverse events, including clinically significant laboratory values
807 related to the study. This medical care for study subjects will be provided regardless of
808 their insurance status. All adverse events classified as serious or severe or
809 possibly/probably related to the trial product will be followed until the subject has
810 recovered and all queries have been resolved. For cases of chronic conditions follow-up
811 until the outcome category is “recovered” is not required, as these cases can be closed with
812 an outcome of “recovering” or “not recovered”. All other adverse events will be followed
813 until the outcome of the event is “recovering” (for chronic conditions), or “recovered” or
814 until the end of the post-treatment follow-up stated in the protocol, whichever comes first,
815 and until all queries related to these AEs have been resolved.

816 **Pregnancy:** Pregnancy test must be negative prior to be enrolled in the study, as per
817 standard care. However, study subjects will be instructed to notify the investigator
818 immediately if they become pregnant. The investigator will report to IRB any pregnancy
819 occurring during the trial period. Reporting of pregnancy by investigator will occur within
820 the same timelines described above for reporting of Adverse Events.

821 **Precautions/Over-dosage:** Precautions and procedures will be observed in the event of
822 overdose of liraglutide provided during the study.

823

824 **Liability and Subject Insurance**

825 The investigator must state that during and following a subject’s participation in trial, the
826 investigator and his/her institution will provide adequate medical care to the study subject
827 for any study-related adverse events, including clinically significant laboratory values
828 related to the study. This medical care for study subjects will be provided regardless of
829 their insurance status.

830 The investigator will be responsible for the conduct of the study and agrees to defend,
831 indemnify, and hold harmless Novo Nordisk, any of its parent companies, affiliates, or
832 subsidiaries, and their respective officers, directors, employees, agents, representatives,
833 distributors, salespersons, customers, licensees, and end-users from and against any claim,
834 suit, demand, loss, damage, expense or liability imposed by any third party arising from or
835 related to: (a) any breach of investigator’s obligations; or (b) investigator’s negligent or
836 grossly negligent use or willful misuse of the study drug, the results, or services derived
837 there from. This indemnification shall not apply in the event and to the extent that a court
838 of competent jurisdiction or a duly appointed arbiter determines that such losses or liability
839 arose as a result of Novo Nordisk’s gross negligence, intentional misconduct, or material
840 breach of its responsibilities.

841 **Publication Plan**

842 Data generated from the study will be published in highly ranked peer reviewed scientific
843 journals, such as Diabetes, Diabetes Care, Obesity or Circulation and presented at national
844 and international meetings, such as ADA 2018-19, ENDO Society 2018-19 and American

845 Heart Association 2018-19. Novo Nordisk will have any manuscripts for publication for
846 review with a right to comment.

847 The investigator will register the study with a publicly assessable database such as
848 clinicaltrials.gov.

849

850 **REGULATORY CONSIDERATIONS**

851 We plan to conduct the trial under an IND exemption. After reviewing 21 CFR
852 312.2(b)(1) and FDA's "Guidance for Clinical Investigators, Sponsors, and IRBs
853 Investigational New Drug Applications (INDs) Determining whether human research
854 studies can be conducted without an IND, September 2013", we believe an IND
855 exemption is applicable to this study as it meets all the criteria, as reported in the table:

857 21CFR 3 12.2 (B) EXEMPTIONS

858 **(1) the clinical investigation of a drug product that is lawfully marketed in the**
 859 **united states is exempt from the requirements of this part if all the following**
 860 **apply:**

861


(i) The investigation is not intended to be reported to FDA as a well-controlled study in support of a new indication for use nor intended to be used to support any other significant change in the labeling for the drug;
	
Meets criteria. This clinical trial is not intended to be reported to the FDA in support of a new indication or change in Victoza labeling.

(ii) If the drug that is undergoing investigation is lawfully marketed as a prescription drug product, the investigation is not intended to support a significant change in the advertising for the product.
	
Meets criteria. This investigation is not intended to support a significant change in the Victoza advertising.

(iii) The investigation does not involve a route of administration or dosage level or use in a patient population or other factor that significantly increases the risks (or decreases the acceptability of the risks) associated with the product
	
Meets criteria. In this clinical trial liraglutide (and the matching placebo) will be administered according to the labeled route and dosage (Pre-filled, multi-dose pen for subcutaneous injection that delivers doses of 0.6 mg, 1.2 mg, or 1.8 mg (6 mg/mL, 3 mL). In this clinical trial liraglutide (and the matching placebo) will be used according to the indications. Liraglutide will be used in adults with type 2 diabetes (T2DM) in adjunct to diet and exercise advices and not as first-line therapy, as study patients will continue their standard diabetes therapy. Hence, liraglutide/placebo is prescribed under inclusion criteria that are the same as for marketed Victoza. Exclusion criteria for liraglutide are also the same as marketed Victoza. This investigation will not increase the risks in the study population.

(iv) The investigation is conducted in compliance with the requirements for institutional review set forth in part 56 and with the requirements for informed consent set forth in part 50;
	
Meets criteria. This study will be reviewed and approved by the University of Miami IRB Institutional Review board prior to study start and will meet with the requirements for informed consent.

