234 Liraglutide. The randomized, double-blind, placebo-controlled study design will allow for
235 an independent and unbiased effect of Liraglutide on study results. In addition, actions to
236 equalize weight loss and maintain similar glucose control between study arms will rule out
237 the confounding effects of these factors on the study outcomes.

238 **Specific Objectives**

239 **Primary Objective:**

240 • to test the hypothesis that liraglutide can reduce the pro-inflammatory
241 transcriptome profile of EAT of subjects with T2DM and CAD.

242 **Secondary Objectives:**

243 • to assess the hypothesis that liraglutide will reduce the ultrasound measured EAT
244 thickness in subjects with T2DM and CAD.
245 • to evaluate the hypothesis that liraglutide can produce more anti-inflammatory
246 effects in the EAT as compared to SAT of subjects with T2DM and CAD.
247 • to test the hypothesis that EAT mRNA and protein expression of GLP-1R will be
248 greater in subjects receiving liraglutide as compared to those continuing their
249 standard therapy

250

251 **Research Design and Methods**

252 **Study Hypotheses**

253 **Hypothesis for Primary Objective:** We hypothesize that EAT inflammatory gene mRNA
254 and protein expression will be lower in subjects receiving additional therapy with
255 liraglutide as compared to those who will continue with their current treatment.

256 **Hypothesis for Second Objectives:** based on our biomolecular and clinical preliminary
257 data, we hypothesize that a) EAT thickness will respond and decrease more on liraglutide
258 than on standard therapy, b) inflammatory genes and protein expression will be different
259 in EAT vs SAT c) EAT GLP-1R expression will be greater in patients on liraglutide vs
260 those on standard therapy.

261

262 **Endpoints**

263 **Primary Endpoint:**

264 • Change from baseline in EAT inflammation (measured as mRNA and protein
265 expression of TNF- α and IL-6) within a minimum of 3 and up to 12 weeks of treatment

266 **Secondary Endpoints:** Change from baseline within a minimum of 3 and up to 12 weeks of
267 treatment for the following parameters:

- 268 • Ultrasound measured EAT thickness
- 269 • SAT inflammation (measured as mRNA and protein expression of TNF- α and IL-6)
- 270 • EAT GLP-1R (measured as mRNA and protein expression of GLP-1R)

271 **Study Type**

272 This is an Investigator Sponsored Study (ISS).

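### No specified analysis tests whether liraglutide acts more in EAT than in SAT, although the samples to be collected would allow it

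*Combined protocol and SAP*

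**What the plan says.** Under Specific Objectives, the second secondary objective is "to evaluate the hypothesis that liraglutide can produce more anti-inflammatory" "effects in the EAT as compared to SAT of subjects with T2DM and CAD". Under Study Hypotheses, the corresponding item (b) is that "inflammatory genes and protein expression will be different" in EAT versus SAT. Items (a) and (c) in the same sentence name liraglutide against standard therapy; (b) names no treatment.

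Under Endpoints, SAT is an endpoint in its own right: "SAT inflammation (measured as mRNA and protein" expression of TNF-α and IL-6. No EAT-minus-SAT difference or EAT/SAT ratio is defined.

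The Power Analysis reports from preliminary data that these genes are "upregulated in subjects with T2DM and CAD and higher in EAT as compared to SAT".

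The end of Statistical Considerations provides Student's t-test or "non-parametric (Mann-Whitney) tests, depending on whether the genes" and proteins are normally distributed, to compare "the effects of treatment (liraglutide versus placebo) on the variables measured". The other analyses are a before-and-after t-test for EAT thickness and univariate regressions of EAT expression on clinical variables. Power is worked out for EAT expression and EAT thickness only.

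Both tissues are taken at surgery from patients in both arms and assayed for the same inflammatory markers (Assessments for Efficacy; Power Analysis).

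**The concern.** The objective asks whether one drug effect (in EAT) exceeds another (in SAT). Hypothesis (b) concerns a main effect of tissue, so it can be confirmed whether or not liraglutide does anything. The planned tests concern the drug effect within a single variable. Neither is the interaction that the objective describes.

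The analyst would be left with one p-value for EAT and one for SAT for each marker. A significant result beside a non-significant one is not a test of whether the two effects differ, but it is the only EAT-against-SAT comparison of drug effect that the planned tests supply. At stake is a claim that liraglutide acts preferentially on epicardial fat. The Abstract and Preliminary Data raise that possibility in hedged terms, and this is the only objective that sets EAT against another depot.

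**Working it through.** **Inputs.** From Statistical Considerations: 20 per arm, two-sided α = 0.05, CV 42%, a difference of 33% also described as approximately 1.3-fold, and log transformation unless values are normal. Assumed, because the documents give no value: within-patient EAT-SAT correlation ρ of 0, 0.5 and 0.7, and the same log SD in both tissues.

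**Scale.** Log SD = √ln(1 + 0.42²) = 0.403. A 33% fall is −ln(0.67) = 0.400, so d = 0.400/0.403 = 0.99. A 1.3-fold difference is ln(1.3) = 0.262, so d = 0.65; as a fall it is 1 − 1/1.3 = 23%. The two descriptions differ, so both are carried through.

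**The plan's own figure.** None is given for this objective. The primary figure (20 per arm, 90% power) is approximately reproduced if 33% means a ratio of 0.67 on the log scale: 88% by normal approximation, 86.5% by noncentral t. At 1.3-fold, noncentral t gives 52%.

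**Hypothesis (b) with an inert drug.** Simulation with no drug effect in either tissue and an assumed tissue difference of 0.3 log units: a pooled within-patient EAT-versus-SAT test is significant in 90% of trials at ρ = 0 and in over 99% at ρ = 0.5 and 0.7. No such test is in the plan; this shows only what the wording of (b) would accept.

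**Separate per-tissue tests, equal true effect in both tissues.** At ρ = 0 the chance of significance in EAT but not SAT is power × (1 − power): 0.865 × 0.135 = 0.117 at a 33% fall, and 0.52 × 0.48 = 0.25 at 1.3-fold. Simulation covers the other correlations:

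| True effect in both tissues | ρ = 0 | ρ = 0.5 | ρ = 0.7 |
|---|---|---|---|
| 33% fall (d = 0.99) | 12% | 9% | 7% |
| 1.3-fold (d = 0.65) | 25% | 17% | 13% |

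These rates are per marker. In the same simulations the direct between-arm contrast of log(EAT) − log(SAT) is significant in about 5%.

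**Power of the direct contrast at 20 per arm.** SD of the within-patient difference = 0.403 × √(2(1 − ρ)) = 0.570, 0.403 and 0.312. Noncentrality = Δ / (SD × √(2/20)), with 38 degrees of freedom.

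| EAT falls 33% and | Δ | ρ = 0 | ρ = 0.5 | ρ = 0.7 |
|---|---|---|---|---|
| SAT does not change | 0.400 | 58% | 86% | 98% |
| SAT responds half as much (log scale) | 0.200 | 19% | 33% | 51% |

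**The case against.** The strongest reply is that the objective itself states the right question, that (b) is loose shorthand placed between two liraglutide hypotheses, and that the data can answer it because both tissues come from the same patients in both arms. The last part stands. A reader might infer that the objective cannot be answered at all, but the documents do not support that: what is missing is a specified contrast, not data. The objective's wording does not fill the gap, since no endpoint or test is attached to it, and a difference score devised later would be post hoc.

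A reader might also infer that the plan intends to claim specificity from significance in one tissue and not the other. It says no such thing. The error rates above belong to a rule that the planned tests leave available, not to one that the sponsor has adopted.

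Nor does the trial's main conclusion rest on this. The primary objective, hypothesis and endpoint concern EAT alone, and the text on fat-depot specificity is hedged.

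The upper end, 25%, needs zero correlation and the smaller effect. That effect is nonetheless the plan's own 1.3-fold, not an arbitrary worst case.

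**Conclusion.** The point holds as a gap between one secondary objective and its analysis. As written, hypothesis (b) could be confirmed by a tissue difference already reported, and no planned test compares the drug effect between tissues. This structural finding rests on the text alone and needs no assumption.

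Its size depends on assumptions. If separate p-values were used, equal effects would look EAT-specific in about 7% to 12% of trials per marker at a 33% fall and 13% to 25% at 1.3-fold. Those ranges assume 20 evaluable patients per arm, log SD 0.403 in both tissues (from a CV based on 5 patients) and ρ between 0 and 0.7. The direct contrast keeps the error at 5%, but it has good power only if SAT responds little and the tissues are well correlated. The sponsor should correct this; the primary analysis is unaffected.

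**What to change.** 1. Restate hypothesis (b): the liraglutide-versus-placebo ratio of expression is lower in EAT than in SAT.
2. For each marker, derive log(EAT) − log(SAT) within each patient from the samples taken at surgery. Compare this difference between arms with a two-sample t-test, or Mann-Whitney if it is not normal.
3. Report the ratio of fold-changes with its 95% CI, and state that tissue specificity will not be inferred from separate EAT and SAT p-values.
4. State the power at 20 per arm for both cases: 58%, 86% and 98% (ρ = 0, 0.5, 0.7) if SAT does not respond, and 19%, 33% and 51% if it responds half as much on the log scale. Add that ρ is assumed and that a non-significant contrast is not evidence of equal effects.

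The cost is a few lines of protocol and SAP text and one derived variable per marker, fixed before unblinding. No further patients, samples or assays are needed.
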